4.2 Exclusion Criteria

A patient will be excluded if any of the following Exclusion Criteria are met:

1. Severe end stage lung disease:
 - a. FVC $\leq 30\%$ *or* FEV1 $\leq 30\%$ *or*
 - b. Requirement of high O₂ requirement ≥ 6 L/min at rest for >1 month before the study enrollment *or*
 - c. Listed for lung transplantation *or*
 - d. PI feels that ILD is severe and end stage fibrosis is such that there is low potential for improvement with any disease modifying intervention.
2. Subjects under the age of 18.
3. Known active current or history of recurrent bacterial, viral, fungal, mycobacterial or other infections (including but not limited to tuberculosis and atypical mycobacterial disease, hepatitis B and C, and herpes zoster, but excluding fungal infections of nail beds).
4. Any major episode of infection requiring hospitalization or treatment with IV antibiotics within 4 weeks of screening.
5. Active TB requiring treatment within the previous 3 years. Patients should be screened for latent TB using PPD/or quantiferon gold within last 1 year and, if positive, treated following local practice guidelines prior to initiating ABT. Patients treated for active tuberculosis with no recurrence in 3 years are permitted.
6. Primary or secondary immunodeficiency (history of or currently active) unless related to primary disease under investigation.
7. Pregnant women or nursing (breast feeding) mothers.
8. History of alcohol, drug or chemical abuse within 1 year prior to screening or any medical condition or physical or psychological state that the PI feels would not allow the subject to safely complete the study.
9. Major surgery (including joint surgery) within 8 weeks prior to screening or planned major surgery within 6 months following randomization.
10. Treatment with any other investigational agent within 4 weeks (or 5 half-lives of the investigational drug, whichever is longer) of screening.

11. Previous treatment with the following cell-depleting therapies, including investigational agents or approved therapies: CAMPATH, anti-CD4, anti-CD5, and anti-CD3.
12. Previous treatment with ABT.
13. History of severe allergic or anaphylactic reactions to monoclonal antibodies.
14. Evidence of serious uncontrolled concomitant cardiovascular, nervous system, renal, hepatic, endocrine (include uncontrolled diabetes mellitus) or gastrointestinal disease (including complicated diverticulitis, ulcerative colitis, or Crohn's disease.)
15. Evidence of concomitant lung disease which PI feels may interfere with clinical assessment of ILD for example severe active COPD, asthma, occupational lung disease, pulmonary sarcoidosis, etc.
16. Prisoners or subjects who are compulsory detained.

4.3 Immunization during Abatacept therapy

Live vaccines should not be given concurrently with ABT or within 3 months of its discontinuation.

4.4 Criteria for Premature Withdrawal

Patients have the right to withdraw from the study at any time for any reason. Every attempt will be made to have all patients complete the remaining study visits as detailed in the Study Schema (Appendix A).

If the patient decides to prematurely discontinue study treatment (“refuses treatment”), he/she should be asked if he/she can still be contacted for further information. The outcome of that discussion should be documented in both the medical records and in the CRF. A complete final evaluation at the time of the patient's withdrawal should be made with an explanation of why the patient is withdrawing from the study.

Before categorizing a patient as lost to follow-up, the investigator must attempt to contact the patient or a responsible relative by telephone followed by registered mail to determine if any new adverse events (AEs) occurred, follow-up of any ongoing AE and to establish as completely as possible the reason for the withdrawal.

When applicable, patients should be informed of circumstances under which their participation may be terminated by the investigator without the patient's consent. The investigator may withdraw patients from the study in the event of intercurrent illness, adverse events, treatment failure, lack of compliance with the study and/or study procedures (e.g., dosing instructions, study visits), or any reason where it is felt by the investigator that it is in the best interest of the patient to be terminated from the study. The reason(s) for withdrawal must be documented and explained to the patient.

If the reason for removal of a patient from the study is an adverse event, the specific event will be recorded in the study database. There should be an attempt to follow the patient until the event has resolved or stabilized.

An excessive rate of withdrawals can render the study non-interpretable; therefore, unnecessary withdrawal of patients should be avoided. Should a patient decide to withdraw, all efforts will be made to complete and report the observations prior to withdrawal as thoroughly as possible.

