3.3.1 Primary Outcome Measures

The primary outcome criteria for efficacy will be the FVC% change from the baseline visit to week 24 between the 2 treatment arms (SOC/placebo vs. SOC/ABT). An intention to treat analysis will be used. Ranked ANCOVA will be used with average standardized rank change in the predicted FVC% as the outcome measure and the standardized rank baseline as a covariate. Primary outcome criteria for safety and tolerability will be adverse events (routine adverse events or tolerability issues and serious adverse event) between the 2 treatment arms (SOC/placebo vs. SOC/ABT). Chi-square (or Fischer exact test) and t-test (or Mann-Whitney) will be used based on data variable and distribution.

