4.5.2 ILD Worsening Criteria

If any one of the criteria is met after 8 weeks of therapy:

- a. FVC% decline $\geq 30\%$ from baseline PFT
- b. HRCT chest suggesting severe worsening in the ILD as compared to baseline (clinician/radiologist interpretation)
- c. Hospitalization with severe ILD with new or increased long term O2 requirement related to worsening ILD
- d. Severe worsening in clinical dyspnea due to ILD as determined by patient and treating physician. Note that meeting “worsening criteria” doesn’t automatically mean administration of rescue therapy. Rescue therapy is given if patient meeting worsening criteria AND treating physician believe clinical disease warrants a change in therapy.

Subjects meeting these criteria will be considered treatment failures but can continue to receive study drug if deemed reasonable by the managing clinician or investigator. If at any time a worsening in condition occurs, the subject should be seen for an unscheduled study visit. A subject irrespective of worsening or rescue medication use, can enter the open label phase (II) of the study at the end of the 24 week period of phase I.

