4.5.3 Rescue Medications

If in the clinical site investigator’s opinion there are complications or worsening of disease (meeting worsening criteria) that necessitate an increase in concomitant immunosuppressive therapy the following guidelines should be followed:

- The steroid dose may be increased by ≤ 20 mg (prednisone equivalent) daily. After 2 weeks of increase the forced corticosteroid taper will commence as noted above. Such patients will remain on the trial protocol (on study drug), and it will not be considered as treatment failure.
- Requirement of additional non-steroid IS therapy or requirement of increase of steroids dose > 20 mg equivalent of prednisone for worsening ILD as rescue therapy (after initial 8 weeks of study drug) will be considered a treatment failure. Such patients can be continued on the trial protocol (on study drug) only if rescue drug include either one of them: MMF, AZA, tacrolimus, cyclosporine, IVIG, methotrexate AND maximum of one non-steroid IS

therapy is given during the trial. Steroids can be concomitantly increased with non-IS agent.

- Note if additional non-steroid IS therapy or increase of steroid dose > 20 mg equivalent of prednisone occurs <8 weeks on study drug, then these patients are not considered treatment failure as not enough time to have outcome assessment.
- Biological drugs, cyclophosphamide, plasmapheresis, are not allowed as rescue therapy and will lead to withdrawal from the trial drug/placebo protocol (i.e stopping trial drug/placebo) for safety reasons. Similarly, more than one non-steroid IS agent is not allowed as rescue therapy and will lead to withdrawal from the trial drug/placebo protocol (i.e. stopping trial drug/placebo). But all patients despite withdrawal from trial drug/placebo will be followed for at least 24 weeks for clinical evaluation. Note withdrawal from trial drug/placebo as above is not considered with withdrawal from the study.

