For example: If a patient is having severe worsening at 3 months while on AZA and the study drug; investigator/treating physician can give rescue steroid increase by 20 mg prednisone (or new prednisone 20 mg if patient was not on steroid) without any changes in the outcome or trial protocol. However, if for some reason the investigator/treating physician needs to start MMF on the patient, then the patient can continue on the trial protocol (on study drug) as long as AZA is stopped (so only one non-steroid immunosuppressive drug is given concomitantly with study drug). Concomitant increase of steroid is OK. Such scenarios should be avoided as these patients will be considered as treatment failure.

Specifically related to this trial, there are several scenarios for subjects as they are followed through the 6 month trial:

1. Subjects can withdraw from the study drug (active drug/placebo) at any time for various reasons deemed appropriate by PI. They are then treated at the discretion of the PI off the study drug, but should continue to be followed at the regular study time points for the duration of the trial for efficacy and safety data monitoring. No randomization scheme will be broken/revealed. Withdrawal from study drug doesn't mean withdrawal from the study.
2. If the criteria for the worsening are formally met but the subject and PI do not feel it is necessary to change therapies other than allowed rescue therapies (as above), then the subject will remain on the trial protocol (study drug). No randomization scheme will be broken/revealed.
3. If criteria for the worsening is formally met and the subject and/or the PI feel that "escape" therapy other than allowable rescue agents is necessary, then the subject will be treated at the discretion of the PI off the trial protocol (withdrawal from study drug), but should continue to be followed at the regular study time points for the duration of the trial for efficacy and safety data monitoring. No randomization scheme will be broken/revealed. Withdrawal from study drug doesn't mean withdrawal from the study.

Refer to Appendix C for rescue medication diagram.

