12.0 STATISTICAL CONSIDERATIONS

12.1 Determination of Sample Size

The sample size is 20 patients with 10 patients in each arm for a 24-week randomized double blind clinical trial. The sample size is justified based on this trial being a proof of concept pilot study. This study will allow us to determine an initial signal for possible efficacy of ABT in Myositis-ILD (Syn-ILD) as well as give safety and tolerability data. Moreover, it will allow us to determine an estimate of the effect size of the study drug and placebo to design a more definitive phase II/III clinical trial. In our cohort about 25% patients with SOC decline by FVC% of $\geq 15\%$ or death or

transplant. Assuming FVC decline by mean of 10% on SOC therapy and trial drug + SOC leads to improvement in FVC% (Even by mean of 5%) we will have >90% power to detect the difference with sample size proposed. Based on our database there is about 25% patients that decline FVC > 10% on SOC for myositis ILD.

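### Section 4.4 lets a failing patient be withdrawn from the study while 4.5.3 keeps such a patient in follow-up to week 24; where a site uses 4.4, a week-24 FVC is lost for a reason tied to the primary outcome.

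*Combined protocol and SAP*

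**What the plan says.** Section 4.4 (Criteria for Premature Withdrawal) gives the investigator discretion: "The investigator may withdraw patients from the study in the event of intercurrent illness, adverse events, treatment failure", among other reasons. The sentence before it says that, when applicable, "patients should be informed of circumstances under which their participation may be terminated by the investigator", and adds that this can happen without the patient agreeing. The same section aims for all patients to finish their visits, discourages unnecessary withdrawal, and asks for a final evaluation at withdrawal. It names no lung function test for that evaluation.

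Section 4.5.3 (Rescue Medications) takes the other line for patients who stop study drug because of rescue therapy: "But all patients despite withdrawal from trial drug/placebo will be followed for at least 24 weeks for clinical evaluation", followed by "Note withdrawal from trial drug/placebo as above is not considered with withdrawal from the study". Its trial-specific scenarios 1 and 3 repeat that patients off study drug "should continue to be followed at the regular study time points for the duration of the trial for efficacy and safety data monitoring".

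Section 4.5.2 (ILD Worsening Criteria) does not require failing patients to stop: "Subjects meeting these criteria will be considered treatment failures but can continue to receive study drug" where the clinician thinks this reasonable.

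The primary analysis in 3.3.1 is the FVC% change from baseline to week 24: "An intention to treat analysis will be used. Ranked ANCOVA will be used with average standardized rank change in the predicted FVC"% as the outcome. Neither 3.3.1 nor 12.3 says what happens to a missing week-24 value. Section 12.1 gives one purpose of the pilot as "it will allow us to determine an estimate of the effect size of the study drug and placebo", for the design of a later trial.

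**The concern.** Two rules cover the same patient. Section 4.5.3 draws an explicit line between leaving study drug and leaving the study, so the word study in 4.4 cannot safely be read as study drug. Five sites could apply the two sections differently.

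Treatment failure is defined in 4.5.2 by FVC decline, HRCT worsening, hospitalization or severe dyspnea. A patient removed under 4.4 for failure is therefore likely to be among those with the worst FVC course, and the value lost is the primary endpoint. A PFT at an unscheduled visit is at the investigator's discretion (7.2), so nothing guarantees a substitute.

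At stake are the intention-to-treat comparison and the effect estimate that 12.1 wants to carry forward. With 10 patients per arm, one or two such losses are enough to move both.

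**Working it through.** **Inputs from the documents.** 10 patients per arm; SOC mean change −10, abatacept plus SOC mean change +5, so a difference of 15; stated power above 90% (all 12.1). The test is ranked ANCOVA with baseline rank as covariate (3.3.1, 12.3).

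**Assumptions.** The documents give no SD, alpha or sidedness. I take two-sided 5%, normal changes and analysis of observed cases.

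**The plan's own figure.** It cannot be reproduced without an SD, but the SD that would support it can be found. For a two-sample t-test the noncentrality is (difference/SD) × √(n/2). With n = 10, 90% power needs difference/SD = 1.534, that is 1.534 × √5 = 3.43. So SD = 15/1.534 = 9.8. I use 9.8, with 7 and 14 as a range.

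**Simulation.** Ordinary least squares of rank(change)/(n+1) on rank(baseline)/(n+1) and arm, where n here is the number of patients analysed; 40,000 trials for the main scenarios. Loss is blind to arm: the worst changes among all 20 are removed.

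| Scenario (true difference 15 unless stated) | Observed difference | Power |
|---|---|---|
| SD 9.8, all values kept | 15.0 | 87% |
| SD 9.8, worst one lost | about 13.4 | 81% |
| SD 9.8, worst two lost | about 12.2 | 74% |
| SD 9.8, worst three lost | about 11.2 | 66% |
| SD 7, none lost / worst two lost | 15.0 / 12.8 | 99% / 96% |
| SD 14, none lost / worst two lost | 15.0 / about 11.8 | 58% / 43% |
| SD 9.8, two random among the worst five | 13.6 | 77% |
| SD 9.8, two random among the worst ten | 15.0 | about 82% |
| SD 9.8, true difference 10, none lost / worst two lost | 10.0 / 7.8 | 54% / 40% |

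With two lost, on average 1.9 are on SOC and 0.1 on abatacept, which is why the difference shrinks. The fall is (15.0 − 12.2)/15.0, about 19%.

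**How many might be lost.** Take only the FVC criterion of 4.5.2, a decline of at least 30%. Read as percentage points, 0.2 patients meet it: difference about 14.5, power 86%. Read as relative to baseline (assumed mean 65, SD 12), 1.9 meet it: about 12.2 and 73%. The other criteria could add patients; the documents give no rate for them.

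**No true effect (both means −10).** Arm-blind loss gives bias 0.0 and significant results favouring abatacept in 2.6% of trials, against a nominal 2.5%.

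**Keeping the patients, with rescue.** Suppose rescue raises the FVC of the two worst patients (SD 9.8, true difference 15):

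| Rise from rescue | Kept: difference, power | Dropped: difference, power |
|---|---|---|
| +5 points | 14.1, 86% | 12.2, 74% |
| +10 points | 13.2, 85% | 12.2, 74% |
| +15 points | 12.3, 81% | 12.2, 74% |
| +20 points | 11.4, 74% | 12.2, 74% |
| full recovery to baseline | 10.8, 70% | 12.2, 74% |

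Keeping them gives the larger difference until rescue adds somewhere between 15 and 20 points.

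**The case against.** The strongest reply is that 4.5.3 already settles the matter. It is written for this trial, covers stopping study drug for any reason the investigator finds appropriate, and states the follow-up rule repeatedly. Section 4.4 is general and permissive. It also uses its terms loosely: one paragraph starts with a patient stopping treatment and ends with that patient leaving the study. Read specific over general, the protocol already asks for what is proposed here.

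Much of this stands. It makes loss a risk and not an expectation. But the precedence is unwritten, and treatment failure is a listed reason in 4.4, so the plea against unnecessary withdrawal does not exclude it.

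The second reply is about size. No document figure supports losing exactly the worst two of 20, observed-case analysis is nowhere stated, and strong rescue recovery removes the advantage of keeping patients. All three stand, and they make the dilution conditional.

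Two stronger readings are tempting. A reader might infer that 4.4 will produce a false positive for abatacept. The trial is double-blind, and arm-blind loss with no true effect gives no bias. A false win needs failing patients to be lost mainly from the abatacept arm: if only that arm loses its worst one or two, false wins rise to 5.8% or 10.5%, but nothing in the documents points to such a pattern. A reader might also count 9.1, whose lead-in speaks of discontinuation from the study, as further bias. Its criteria are hypersensitivity and pregnancy, which are not tied to FVC, so it shares the wording conflict only.

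**Conclusion.** The contradiction is in the text and no passage resolves it. Whether it costs anything depends on a site using 4.4 against 4.5.3, which may never happen.

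If it does happen, the week-24 FVC is lost for a reason related to the primary outcome and the intention-to-treat comparison is weakened. Dilution follows only if the drug works, observed cases are analysed and rescue does not largely reverse the decline. On those terms the loss is about 1.6 to 3.8 points of a 15-point difference (15.0 − 13.4 and 15.0 − 11.2) and 6 to 21 points of power for one to three patients. It is negligible if only 0.2 patients are lost, and nil for bias if there is no true effect. With rescue gains of about 20 points or more, collecting the values no longer gives a larger difference, though it still preserves the comparison as randomised.

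The SD, the number lost and which patients are lost are all assumed, so the sizes are illustrative. The sponsor should make the change because it is cheap and the contradiction is certain; confidence in a material effect is medium.

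**What to change.** Reconcile 4.4 and the lead-in of 9.1 with 4.5.3, so that removal initiated by the investigator for treatment failure, worsening or adverse events ends study drug only. State that the week-24 PFT is collected in every randomised patient who is alive and has not withdrawn consent. Nothing changes in when or why study drug is stopped.

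The cost is a few sentences. The week-24 PFT is already scheduled in 7.2 and the follow-up is already set in 4.5.3, so no visit or test is added. The downside is that collected values include the effect of any rescue therapy.

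A separate, secondary point does not carry this one: before unblinding, 3.3.1 and 12.3 should state how a week-24 FVC that is still missing enters the ranked ANCOVA, by reason (death or transplant; too ill for spirometry; consent withdrawn or lost to follow-up). Add a complete-case sensitivity analysis and report missing values by arm and reason. The ranking is the sponsor's choice, but it has a price: assigning the worst rank makes the endpoint a composite and, with 10% events in each arm, takes power from 87% to 63–71%.

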4.5 Definition of Worsening Criteria

4.5.1 Myositis Worsening Criteria

If any one of the criteria is met after 8 weeks of therapy:

- a. Physician global worsening of ≥ 2 cm on the 10 cm VAS and/or worsening of the manual muscle testing by $\geq 20\%$, or
- b. Global extra muscular organ disease activity worsening by ≥ 2 cm on a 10 cm VAS on MDAAT, or
- c. 3 of 6 CSM worse by $\geq 30\%$.

4.5.2 ILD Worsening Criteria

If any one of the criteria is met after 8 weeks of therapy:

- a. FVC% decline $\geq 30\%$ from baseline PFT
- b. HRCT chest suggesting severe worsening in the ILD as compared to baseline (clinician/radiologist interpretation)
- c. Hospitalization with severe ILD with new or increased long term O2 requirement related to worsening ILD
- d. Severe worsening in clinical dyspnea due to ILD as determined by patient and treating physician. Note that meeting “worsening criteria” doesn’t automatically mean administration of rescue therapy. Rescue therapy is given if patient meeting worsening criteria AND treating physician believe clinical disease warrants a change in therapy.

Subjects meeting these criteria will be considered treatment failures but can continue to receive study drug if deemed reasonable by the managing clinician or investigator. If at any time a worsening in condition occurs, the subject should be seen for an unscheduled study visit. A subject irrespective of worsening or rescue medication use, can enter the open label phase (II) of the study at the end of the 24 week period of phase I.

4.5.3 Rescue Medications

If in the clinical site investigator’s opinion there are complications or worsening of disease (meeting worsening criteria) that necessitate an increase in concomitant immunosuppressive therapy the following guidelines should be followed:

- The steroid dose may be increased by ≤ 20 mg (prednisone equivalent) daily. After 2 weeks of increase the forced corticosteroid taper will commence as noted above. Such patients will remain on the trial protocol (on study drug), and it will not be considered as treatment failure.
- Requirement of additional non-steroid IS therapy or requirement of increase of steroids dose > 20 mg equivalent of prednisone for worsening ILD as rescue therapy (after initial 8 weeks of study drug) will be considered a treatment failure. Such patients can be continued on the trial protocol (on study drug) only if rescue drug include either one of them: MMF, AZA, tacrolimus, cyclosporine, IVIG, methotrexate AND maximum of one non-steroid IS

therapy is given during the trial. Steroids can be concomitantly increased with non-IS agent.

- Note if additional non-steroid IS therapy or increase of steroid dose > 20 mg equivalent of prednisone occurs <8 weeks on study drug, then these patients are not considered treatment failure as not enough time to have outcome assessment.
- Biological drugs, cyclophosphamide, plasmapheresis, are not allowed as rescue therapy and will lead to withdrawal from the trial drug/placebo protocol (i.e stopping trial drug/placebo) for safety reasons. Similarly, more than one non-steroid IS agent is not allowed as rescue therapy and will lead to withdrawal from the trial drug/placebo protocol (i.e. stopping trial drug/placebo). But all patients despite withdrawal from trial drug/placebo will be followed for at least 24 weeks for clinical evaluation. Note withdrawal from trial drug/placebo as above is not considered with withdrawal from the study.

For example: If a patient is having severe worsening at 3 months while on AZA and the study drug; investigator/treating physician can give rescue steroid increase by 20 mg prednisone (or new prednisone 20 mg if patient was not on steroid) without any changes in the outcome or trial protocol. However, if for some reason the investigator/treating physician needs to start MMF on the patient, then the patient can continue on the trial protocol (on study drug) as long as AZA is stopped (so only one non-steroid immunosuppressive drug is given concomitantly with study drug). Concomitant increase of steroid is OK. Such scenarios should be avoided as these patients will be considered as treatment failure.

Specifically related to this trial, there are several scenarios for subjects as they are followed through the 6 month trial:

1. Subjects can withdraw from the study drug (active drug/placebo) at any time for various reasons deemed appropriate by PI. They are then treated at the discretion of the PI off the study drug, but should continue to be followed at the regular study time points for the duration of the trial for efficacy and safety data monitoring. No randomization scheme will be broken/revealed. Withdrawal from study drug doesn't mean withdrawal from the study.
2. If the criteria for the worsening are formally met but the subject and PI do not feel it is necessary to change therapies other than allowed rescue therapies (as above), then the subject will remain on the trial protocol (study drug). No randomization scheme will be broken/revealed.
3. If criteria for the worsening is formally met and the subject and/or the PI feel that "escape" therapy other than allowable rescue agents is necessary, then the subject will be treated at the discretion of the PI off the trial protocol (withdrawal from study drug), but should continue to be followed at the regular study time points for the duration of the trial for efficacy and safety data monitoring. No randomization scheme will be broken/revealed. Withdrawal from study drug doesn't mean withdrawal from the study.

Refer to Appendix C for rescue medication diagram.

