12.3 Methods of Analysis

Primary End Point:

The primary end point for statistical analysis will be the percent FVC changes from baseline to week 24 between the 2 treatments arms (SOC/placebo vs. SOC/ABT). Ranked ANCOVA, with average standardized rank change in the predicted FVC% as the outcome measure and the standardized rank baseline as a covariate will be used. Primary outcome criteria for safety and

tolerability will be adverse event (routine adverse events or tolerability issues and serious adverse event) between the 2 treatment arms (SOC/placebo vs. SOC/ABT). Chi-square (or Fischer exact test) and t-test (or Mann-Whitney) will be used based on data variable and distribution. Patients will be stratified for sub-analysis based on their SOC drug

Secondary Analysis (SOC/placebo vs. SOC/ABT) for Syn-ILD:

- a. Time to progression free survival where progression is defined as first occurrence of any of the following: death or lung transplant or $FVC \geq 10\%$ decline *or* $FVC \geq 5\%$ decline with $DLCO \geq 15\%$ decline. This will be done using Cox proportional hazards model and controlling for baseline demographics and $FCV\%$.
- b. Change in dyspnea, as measured by University of California San Diego Shortness of Breath Questionnaire (UCSD SOBQ) (range 0-120, higher score is worsening dyspnea), will be done using Mann-Whitney test.
- c. Time to improvement in $FVC\%$ by $\geq 10\%$. This will be done using Kaplan Meier survival curve and Cox's proportional hazards model after controlling for co-variates.
- d. Rates of death or requiring lung transplant using Chi-square (Fischer exact) test.
- e. Other individual PFT variables (FEV1%, DLCO%) similar to analysis done for primary outcome of $FVC\%$.
- f. Qualitative changes in HRCT chest over 6 months in the two arms using chi-square (or Fischer exact) test. Changes in semi-qualitative scoring of fibrosis over 6 months based on HRCT chest scan images collected from all sites and centrally read by an expert blinded radiologist, will be done as a separately and analyzed using analysis strategy similar to primary outcome.
- g. Steroid-sparing effect (calculated using prednisone dose equivalents) using paired t-test.
- h. Frequency of treatment failures: a) patient meeting worsening criteria or withdrawal due to worsening ILD anytime during the trial or b) $FVC\%$ worsening by 10% at 6 months, c) death or transplant within 6 months. Chi-square test will be used to compare between the two groups.

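### Secondary endpoint h (treatment failure) classifies one group in two opposite ways: patients who meet a 4.5.2 ILD worsening criterion after week 8 and are rescued with only a ≤20 mg/day prednisone increase

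*Combined protocol and SAP*

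**What the plan says.** **The rule based on the criteria.** Section 4.5.2 lists four ILD worsening criteria, any one of which counts once 8 weeks of therapy have passed. It then says: "Subjects meeting these criteria will be considered treatment failures but can continue to receive study drug". It makes no exception for the rescue given. Endpoint h, part (a), in sections 3.3.2, 12.2.2 and 12.3 also counts a "patient meeting worsening criteria or withdrawal due to worsening ILD anytime during the trial". Part (b) adds a 10% worsening of FVC% at 6 months, and part (c) adds death or transplant within 6 months. The comparison is by chi-square test.

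**The rule based on the rescue.** Section 4.5.2 ties rescue to the criteria: "Rescue therapy is given if patient meeting worsening criteria AND treating physician believe clinical disease warrants a change in therapy". Section 4.5.3 opens on patients with "complications or worsening of disease (meeting worsening criteria) that necessitate an increase in concomitant immunosuppressive therapy". Its first bullet allows a steroid increase of up to 20 mg/day prednisone equivalent and says: "Such patients will remain on the trial protocol (on study drug), and it will not be considered as treatment failure". Its second bullet makes added non-steroid therapy, or a larger steroid increase, for worsening ILD after week 8 a failure. Its third bullet deals with rescue before week 8.

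**The example in 4.5.3.** A patient on azathioprine worsens severely at 3 months. Adding 20 mg prednisone is allowed "without any changes in the outcome or trial protocol". A switch to mycophenolate is discouraged: "Such scenarios should be avoided as these patients will be considered as treatment failure".

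**The concern.** Both rules are stated outright, and they give opposite answers for the same patient. Analysts will know who met a criterion and what was given, but nothing in the available text tells them which sentence decides the endpoint. If this is left open, the choice could be made once the allocation is known.

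The two rules also measure different things. Under 4.5.2 and h(a), classification follows from the patient's condition. Under the first bullet of 4.5.3, the physician's choice of rescue decides it, and the example steers sites towards the rescue that is said to leave the outcome alone. Section 12.1 says the pilot should "determine an estimate of the effect size of the study drug and placebo to design a more definitive phase II/III clinical trial", so a failure rate whose definition is unsettled would be a poor input to later planning if it were used for that.

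**Working it through.** The plan gives no figure for this endpoint, so there is none to reproduce. The check is a comparison of the texts, followed by simple arithmetic on what one patient is worth.

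**Step 1. One patient, two rules.** Take a patient whose dyspnea from ILD worsens severely at week 12 (4.5.2 criterion d), who gets 20 mg/day extra prednisone and nothing else, and whose FVC% at 6 months has not worsened by 10%.

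| Text | Classification |
|---|---|
| 4.5.2, closing paragraph | Failure |
| 12.3 h(a); same in 3.3.2 and 12.2.2 | Failure |
| 4.5.3, first bullet | Not a failure |
| 4.5.3, example at 3 months | Outcome unchanged |

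**Step 2. Readings that would remove the conflict.**
- *The first bullet applies only before week 8.* It carries no time limit, the third bullet handles that period separately, and the example is at 3 months.
- *Only the steroid increase, as an act, is not a failure.* The example contrasts the steroid patient, whose outcome does not change, with the mycophenolate patient, who becomes a failure. That contrast is empty if the steroid patient has already failed by meeting 4.5.2.
- *The first bullet covers only complications outside 4.5.2.* The opening of 4.5.3 expressly includes patients who meet the criteria, and 4.5.2 makes meeting them a condition of rescue.

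**Step 3. Who is affected.** A patient must meet a 4.5.2 criterion after week 8, receive only a ≤20 mg/day steroid increase, and fail by no other route. Section 3.1.1 (steroid dosing during flare) separately allows an increase of up to 20 mg/day on the investigator's opinion, without requiring 4.5.2 to be met. Those increases are outside the conflict.

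**Step 4. Size.** Section 12.1 gives 10 patients per arm. Let f be the number of failures by other routes and k the number of affected patients, with subscripts P (placebo) and A (abatacept).
- Difference with affected patients counted: (f_P + k_P − f_A − k_A)/10
- Difference with them not counted: (f_P − f_A)/10
- Gap between the rules: (k_P − k_A)/10

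So each affected patient moves that arm's rate by 1/10 = 10 points, and the gap is zero when k_P = k_A.

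**Step 5. Illustration.** All counts are assumed, because the documents give no rescue rate. Take f_P = 3, close to the 25% on standard of care that 12.1 reports as declining, f_A = 1 and k_A = 0. Intervals are Newcombe 95%.

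| k_P | Placebo v abatacept if counted | Difference (95% CI) | Fisher p |
|---|---|---|---|
| 0 | 3/10 v 1/10 | 20 points (−16 to 51) | 0.582 |
| 1 | 4/10 v 1/10 | 30 points (−8 to 60) | 0.303 |
| 2 | 5/10 v 1/10 | 40 points (0 to 68) | 0.141 |

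If they are not counted, every row returns to the first. Fisher's p is non-significant under both rules. With one affected patient in each arm, counting gives 4/10 v 2/10, a difference of (4 − 2)/10 = 20 points, the same as 3/10 v 1/10.

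**The case against.** **The Appendix C diagram may settle it.** Section 4.5.3 refers to that diagram, which is not in the text available to us, so its absence here is no defect of the plan. This stands as a limit: the diagram may favour one rule. It cannot make the sentences in 4.5.2 and 4.5.3 agree, so one of them would still need changing.

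**The group is small.** This stands. Severe HRCT worsening, or hospitalization with a new oxygen requirement, seems unlikely to be managed with ≤20 mg prednisone alone, and some patients that ill will also meet h(b). The illustration puts every affected patient on placebo, which is the unfavourable case.

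**The authors may have meant the 4.5.3 rule.** It is the more specific text, and its bullets and example grade failure by the rescue needed. This is a fair reading of intent, and the fix should leave the sponsor that route.

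**Stronger readings to resist.**
- A reader might infer that the conflict could decide significance. With the uncorrected chi-square, 4/10 v 0/10 gives p = 0.025 and 3/10 v 0/10 gives 0.060. Those counts are chosen, the expected failures per arm are only 2 and 1.5, and Fisher's p is 0.087 and 0.211, non-significant under both. Counts can be picked where Fisher's test also crosses 0.05 (5 v 0, p = 0.033; 4 v 0, p = 0.087), but nothing in the documents makes them likely.
- A reader might infer that the size of a later trial hangs on this. Section 12.1 discusses power only for FVC% and does not say a later trial would be powered on treatment failure.
- A reader might infer that most steroid rescues are affected. The separate allowance in 3.1.1 leaves some outside, and no rescue rate is given.

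**Conclusion.** The contradiction is real and confined to patients who meet a 4.5.2 criterion after week 8, receive only a ≤20 mg/day prednisone increase, and do not meet h(b) or h(c). For them 4.5.2 and h(a) say failure, while the first bullet and example of 4.5.3 say non-failure. How many there will be is unknown. The 10-point effect per patient assumes all 10 patients per arm stay in the denominator. Any change in the between-arm difference further assumes that affected patients are unequally split. With an equal split, or none at all, the difference is the same under both rules. The primary FVC% analysis is not touched. This is a change worth making because the cost is trivial and the choice should not be open after unblinding. It does not threaten the trial's main conclusion.

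**What to change.** Before unblinding, make one rule primary for endpoint h.

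**Preferred: 4.5.2 and h(a).** The analysis section already states this rule, and classification then does not depend on which rescue the physician picks.
1. Reword the first bullet of 4.5.3 so that a steroid increase of ≤20 mg/day is not a failure only when no 4.5.2 criterion is met.
2. In the example, strike the reference to the outcome, so that only the trial protocol is said to be unchanged.
3. Report endpoint h once more with the ≤20 mg steroid-only patients counted as non-failures.
4. Bring Appendix C into line.

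**Alternative, if the sponsor intended the 4.5.3 rule:** amend the failure sentence in 4.5.2 and part (a) of endpoint h in 3.3.2, 12.2.2 and 12.3, bring Appendix C into line, and report the 4.5.2 count as the sensitivity row.

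Either route costs a few sentences and one table row. No patients, visits or procedures are added, and the rules for stopping study drug stay as they are.
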